#### 8.2. Study Site Activation

During the activation process (prior to subject enrollment), the Sponsor will train study site personnel on the clinical investigation plan, on relevant standards and regulations, informed consent, and on data collection and reporting tools. If new members join the study site team, they will receive training on the applicable study requirements relevant to their role before contributing to the study.

Prior to performing study related activities, all regulatory requirements shall be fulfilled, including, but not limited to the following:

- EC approval (and voting list, as required by local law) of the current version of the CIP and Informed Consent (IC).
- CA approval or notification (as required per local law)
- Fully executed CTA
- Financial disclosure
- CV of investigators and key members of the investigation study site team (as required). The signature on the CV must be dated within 3 years prior to the date of activation of the study site.
- Documentation of delegated tasks
- Documentation of study training
- Additional requirements imposed by local regulations, the EC and CA shall be followed, if appropriate.

In addition, all participating study site staff must be trained on the current version of the CIP as well as on the applicable study requirements depending on their role and must be delegated by the principal investigator to perform study related activities.

The Sponsor will provide the study site with documentation of study site/investigator readiness- a site activation letter; this letter must be received prior to performing any study related activities.

#### 8.3. Role of the Sponsor Representatives

In addition to performing monitoring and auditing activities, Sponsor representatives may provide support to the study site, as required for the study, under the supervision of the Principal Investigator, including but not limited to:

 Provide study training relevant and pertinent to the involvement of personnel conducting study activities and investigator responsibilities

Medtronic

Version 4.0 Version Date: 16Jun2022 Page 24 of 75

#### 9. Selection of Subjects

#### 9.1. Study Population

Up to 15 subjects at high risk for CRC (as defined by inclusion criterion #2) will be enrolled to this study.

#### 9.2. Subject Enrollment

Written ICF will be obtained from each subject prior to performing any screening assessments. Once ICF is obtained, subjects will be screened to ensure they meet all of eligibility criteria prior to study enrollment. A subject is considered enrolled in the study once the ICF is signed and it is determined that all eligibility criteria are met.

#### 9.3. Inclusion Criteria

- 1. Male or female adults ages 45-75 years
- 2. Subject is classified as being at high risk for CRC due to one (or more) of the following risk factors:
  - A personal history of colorectal polyps
  - A first-degree family history of colorectal cancer
  - Family/personal inherited syndrome (Lynch syndrome, Familial adenomatous polyposis {FAP}, other inherited syndromes linked to colorectal cancer)
  - Subject with currently suspected or diagnosed rectal bleeding, including positive FIT or positive fecal DNA test
  - Subjects under surveillance for CRC (last OC≥1.5 years)
- 3. Subject is willing and able to participate in study procedures, understand and sign the informed consent

#### 9.4. Exclusion Criteria

- 1. Subject has a previous history or suspicion of inflammatory bowel or Crohn's disease, ulcerative Colitis or indeterminant Colitis
- 2. Subject has congestive heart failure or recent myocardial infarction (<3month)
- 3. Subject with moderate/severe renal disease and/ or severe hepatic impairment
- 4. Subject has uncontrolled diabetes
- 5. Subject has a severe, life-threatening disease
- 6. Subject with known gastrointestinal motility disorders
- 7. Subject has known delayed gastric emptying

- 8. Subject has undergone surgery of the luminal gastrointestinal (GI) tract, from esophagus to the rectum, other than uncomplicated appendectomy or cholecystectomy.
- 9. Subject with any current condition believed to have an increased risk of capsule retention such as suspected or known bowel obstruction or pseudo-obstruction, stricture, or fistula (symptoms such as severe abdominal pain with accompanying nausea or vomiting)
- 10. Subject with dysphagia, any swallowing disorder, or any major gastrointestinal motility disorder
- 11. Subject has a history of inadequate bowel preparation for colon imaging with colonoscopy, CTC, CCE, or DCBE (self-reporting)
- 12. Subject with known or suspected constipation history as defined by the following: as needing the use of medication (prescription or OTC) for management of constipation, or fewer than 3 BM/week regardless of medication use
- 13. Subject with a cardiac pacemaker or other implanted electromedical device
- 14. Subject with planned MRI examination within 7 days after ingestion of the capsule
- 15. The subject is taking antidepressant medicine or a medicine for psychiatric illness, such as:
  - selective serotonin reuptake inhibitor (SSRI)- as fluoxetine, fluvoxamine, paroxetine, sertraline, citalopram, escitalopram and zimeldine; - bupropion, venlafaxine, mirtazapine, clomipramine, buspirone; -
  - medicines classified as Monamine Oxidase Inhibitors (often used for treating depression).
- 16. Subject has glucose-6-phosphate dehydrogenase (G6PD) deficiency and/or allergic to peanut/soya
- 17. Subject consumes any of the medicinal products which interacts with MB-MMX, as per MB-MMX label and Investigator's discretion
- 18. Subject with allergies or known contraindication to the device, medications or preparation agents used in the procedure as described in the relevant instructions for use/ package inserts
- 19. Subject use of opioid medication on a regular basis and requires medication to treat opioid induced constipation
- 20. Subject currently participating in another gastrointestinal clinical study (investigational drug or device) that might interfere with results of study
- 21. Females who are pregnant or breastfeeding at time of bowel prep

MDT20062 SPICE Clinical Investigation Plan			
Version 4.0	Version Date: 16Jun2022	Page 26 of 75	Medtronic

- 22. Any condition which precludes compliance with study and/or device instructions based on the clinical judgment of the investigator
- 23. Subject who is considered to be part of a vulnerable population (e.g. prisoners or those without sufficient mental capacity)
- 24. Medtronic employees

Version 4.0 Version Date: 16Jun2022 Page 27 of 75

Medtronic

#### **10.Study Procedures**

The study consists of a screening – enrollment phase, bowel preparation phase, including MB-MMX tablets administration, followed by the PillCam™ Colon endoscopy procedure visit and a post procedure telephone follow up visit, as described in Table 1- Schedule of events and data collection:.

#### 10.1. Schedule of Events & Data collection

The study assessment in table 1 indicates the observations/ assessments/ data collection to be conducted throughout the study period.

Table 1- Schedule of events and data collection:

	Screening/ Enrollment	Preparation	Procedure Visit	Follow Up Visit
↓ Procedure Visit ⇒	V1		V2	V3
Time Schedule (Days)	(-30)-(-3) 	(-3)-0 	0	7±2
Inform consent	Х			
Eligibility criteria	Х			
Demographic data	Χ			
Medical History	Х			
Concomitant medication	Χ		X	
Vital Signs and height/weight measurements	Х		Х	
Urine Pregnancy test (when applicable)	Х	X 		
Provide Preparation materials (including MB-MMX) and subject instructions form	Х			
Low Fiber Diet		X		
Bowel Preparation intake		Х		
MB-MMX intake		X 		
Bowel preparation and MB-MMX compliance verification			Х	
Prucalopride administration			Х	
CCE administration			X	
Device Deficiencies			X	Х
Study Deviations	Х	Х	X	Х
AEs collection		Х	Х	X
Study exit				Х

<sup>1 Screening/enrollment process may start 3-30 days prior to visit 2.

<sup>2Preparation starts 3 days prior to visit 2

<sup>3 Urine Pregnancy test must be performed at day (-1) prior to the bowel prep/MB-MMX intake (when applicable).

<sup>4MB-MMX is administrated at day (-1).

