## MDT20062 SPICE Clinical Investigation Plan Version 4.0 Version Date: 16Jun2022 Page 12 of 75 Medtronic

	17. Subject consumes any of the medicinal products which		
	interacts with MB-MMX, as per MB-MMX label and		
	Investigator's discretion		
	18. Subject with allergies or known contraindication to the		
	device, medications or preparation agents used in the		
	procedure as described in the relevant instructions for		
	use/package inserts.		
	19. Subject use of opioid medication on a regular basis and		
	requires medication to treat opioid induced constipation		
	20. Subject currently participating in another gastrointestinal		
	clinical study (investigational drug or device) that might interfere with results of study		
	21. Females who are pregnant or breastfeeding at time of		
	bowel prep		
	22. Any condition which precludes compliance with study		
	and/or device instructions based on the clinical judgment		
	of the investigator		
	23. Subject who is considered to be part of a vulnerable		
	population (e.g. prisoners or those without sufficient		
	mental capacity)		
	24. Medtronic employees		
Study Procedures and	Day -30 to (-3)- Screening visit:		
Assessments	Obtain written informed consent		
	Confirm inclusion/exclusion		
	Medical history+ concomitant medication+ demographics		
	Vital signs		
	Urine Pregnancy test (when applicable)		
	Provide study bowel preparation martials & MB-MMX		
	tablets		
	Day (-3) - (-2) - low fiber diet		
	Day -1:		
	Clear liquid diet		
	
 
Urine Pregnancy test (when applicable)
 
		
	Bowel prep- 4L PEG+ MB-MMX (in accordance to the MB-		
	MMX IFU):		
	William Cy.		
	The first dose of 3 MB-MMX tablets should be		
	
 
The first dose of 3 MB-MMX tablets should be taken after drinking at least 1 L of PEG;
 
		
	The first dose of 3 MB-MMX tablets should be		

Version 4.0 Version Date: 16Jun2022 Page 13 of 75

Medtronic

	
 
The last dose of 2 MB-MMX tablets should be taken 1 hour after the second dose.
 
Day 0:         
 
Clear liquid diet
 
Vital signs
 
1 tablet of prucalopride 1mg
 
 
 
CE procedure, including boosts intake.
 

	Day 5-9: Follow-up phone call

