## MDT20062 SPICE Clinical Investigation Plan Version 4.0 Version Date: 16Jun2022 Page 28 of 75 Medtronic

#### 10.2. Subject Screening (visit 1)

All subjects that are considered for the study should be included on the study screening log. The reason for non-eligibility, as determined by the Investigator, should be recorded on the study screening log. The screening log serves as a method for the Sponsor to assess selection bias in the trial.

During the screening visit, the investigator will obtain patient's written informed consent, after the subject had an ample time and opportunity to read and understand the ICF, verify that the subject does not have any contraindications for the PillCam™ Capsule Endoscopy procedure, and assess each subject for eligibility based on the inclusion/exclusion criteria.

To determine subject eligibility, baseline information will be collected as outlined in Table 1- Schedule of events and data collection:. Informed consent, vital signs, medical history, concomitant medications, urine pregnancy test (performed in women with childbearing potential) and demographic information will be collected during the visit. Study medications required for the preingestion procedure will be provided to eligible subjects during this visit.

Data of screen failure subjects will not be captured within the Electronic Case Report Form (eCRF). Their signed ICF and Inclusion-Exclusion criteria evaluation will be kept on site.

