#### 17.Appendices

Appendix A: SPICE Study- Bowel Preparation/MB-MMX administration Schedule

PEG> Citrafleet/Picosalax				
Time		Activity		
Day (-3)	All day	Low-fiber diet Low-fiber diet	No nuts, seeds, granola, fruit with skin or seeds, any type of legume, whole grains, anything with red or	
Day (-2)			purple dye, vegetables as Corn, potatoes with skin, tomatoes, cucumbers with seeds and peel, etc.	
	All day	Water	At least 10 glasses	
	All Day	Clear liquid diet	No solid food	
	18:00-19:00	Bowel prep	1L of PEG solution (i.e. Solución evacuante)	
	19:00-20:00	Bowel prep	1L of PEG solution	
Day ( 1)	20:00	MB-MMX 1 st dose	3 MB-MMX tablets after drinking at least 1L of PEG	
Day (-1)	20:00-21:00	Bowel Prep	1L of PEG solution	
	21:00	MB-MMX 2 nd dose	3 MB-MMX tablets 1h after the 1st dose	
	21:00-22:00	Bowel Prep	1L of PEG solution	
	22:00	MB-MMX 3 rd dose	2 MB-MMX tablets 1h after the 2 nd dose	
	All day	Clear liquid diet	No solid food	
	07:00-	Tablet	1 Prucalopride (i.e. Resolor) tablet of 1 mg	
	08:00	PillCam™ capsule	45 – 90 min after Prucalopride consumption	
	08:45 - 09:15 DR alert #1	Boost 1 (G2SB) *	1 sachet of Citrafleet/Picosalax, diluted with water- 150ml	
	09:15 - 10:15	Water	1L water- through 1h duration after DR alert #1	
Day 0	11:45-12:00	Boost 2	1 sachet of Citrafleet/Picosalax, diluted with water-	
Day o	DR alert #2		150ml, 3h after alert #1	
	12:00-13:00	Water	1L water- Through 1h duration after DR alert #2	
	13:45	Suppository	Bisacodilo/ Contalax 10 mg (Bisacodyl)	
	DR alert #3		2h after alert #2	
	15:45	Meal	Light meal	
	DR alert #4		2h after alert #3	

\* Time of G2S is estimated. 10 mg Metoclopramide (i.e. Primperan/ Pramin will be administrated in case the capsule fails to enter SB within 1h from ingestion (alert 0)

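### No medication review is scheduled between screening and MB-MMX intake, so exclusions 15 and 17 go unchecked for 2 to 29 days before the dose

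*Protocol*

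**What the plan says.** Protocol 10.1, Table 1, allows screening (V1) from day -30 to day -3. It marks eligibility at V1 only, and concomitant medication at V1 and at the day 0 procedure visit (V2). The Preparation column has neither mark. The Synopsis lists "Medical history+ concomitant medication+ demographics" under the screening visit. Its day 0 list and section 10.4 do not mention a medication review.

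MB-MMX is handed out at screening: "Study medications required for the preingestion procedure will be provided to eligible subjects during this visit" (10.2). Footnote 4 of Table 1 states "MB-MMX is administrated at day (-1". Appendix A gives the first dose at 20:00 as "3 MB-MMX tablets after drinking at least 1L of PEG", then 3 tablets at 21:00 and 2 at 22:00.

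Two exclusions in 9.4 concern current medication, and neither has a time point:
- Exclusion 17: "Subject consumes any of the medicinal products which interacts with MB-MMX, as per MB-MMX label and Investigator's discretion".
- Exclusion 15: "The subject is taking antidepressant medicine or a medicine for psychiatric illness", followed by a list of drugs. No reason is given for it.

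Pregnancy is handled differently. Exclusion 21 reads "Females who are pregnant or breastfeeding at time of bowel prep", and footnote 3 of Table 1 says "Urine Pregnancy test must be performed at day (-1) prior to the bowel prep/MB-MMX intake (when applicable".

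**The concern.** A subject can be eligible at screening and start a barred medicine before day -1. Unless the subject volunteers this, all 8 tablets are taken before anyone is due to ask. The day 0 entry can record the exposure but cannot prevent it. Exclusion 17 also relies on the investigator's discretion, which cannot be used on a drug the investigator does not know about.

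The issue is patient safety. Section 11.1 acknowledges possible interactions with concomitant treatments but refers to manuals for the details. Section 6.2 describes MB-MMX intake as additional to standard care, so the study itself creates the exposure. Any effect on the descriptive percentage of subjects with an adverse event is secondary.

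**Working it through.** The plan states no figure to reproduce. The first two steps come from the documents; the last three are illustrations on assumed values.

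**1. Length of the gap** (Table 1: screening day -30 to -3, intake day -1).
- Earliest screening: -1 - (-30) = 29 days.
- Latest screening: -1 - (-3) = 2 days.

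**2. Timing of the next review** (Appendix A). The last tablets are at 22:00 on day -1 and the first timed step on day 0 is at 07:00. The review therefore comes at least 9 hours after dosing is complete.

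**3. Chance of at least one exposed subject in 15.** The documents give no start rates. Let *p* be the assumed proportion starting a barred drug over 29 days, at a constant rate. The 2-day proportion is 1 - (1 - *p*)^(2/29), which is 0.00035, 0.00069 and 0.0021 for the three values of *p* below. With *q* the proportion for the gap in question, the chance of at least one is 1 - (1 - *q*)^15. These are upper bounds, because they assume that no subject volunteers the new medicine.

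| Assumed *p* | All gaps 29 days | All gaps 2 days |
|---|---|---|
| 0.5% | 7.2% | 0.5% |
| 1% | 14.0% | 1.0% |
| 3% | 36.7% | 3.1% |

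**4. The same if half of these subjects volunteer the medicine** (assumed; *q* is halved).

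| Assumed *p* | All gaps 29 days | All gaps 2 days |
|---|---|---|
| 0.5% | 3.7% | 0.3% |
| 1% | 7.2% | 0.5% |
| 3% | 20.3% | 1.6% |

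**5. Time left unchecked after a day -1 call.** A call between 08:00 and 18:00 (assumed hours) is 12 to 2 hours before the 20:00 dose.
- 29-day gap (696 h): 2/696 = 0.3% to 12/696 = 1.7% remains.
- 2-day gap (48 h): 2/48 = 4% to 12/48 = 25% remains. Taking exactly 48 h implies screening at 20:00 on day -3. An earlier clinic hour lengthens the gap and lowers these percentages.

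**The case against.** **Harm is not documented.** The only MB-MMX events the protocol names are discoloured urine and faeces, described as mostly mild. It does not say that any exclusion 15 drug interacts with MB-MMX. This stands: the harm cannot be sized, and exclusion 15 is included because the protocol bars those medicines, not because an interaction is shown.

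**The probabilities rest on assumptions.** They run from 0.3% to 37%, so they cannot set the priority. This also stands. The case rests on the missing check.

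**Pregnancy is a different case.** A subject may not know she is pregnant, but does know of a new medicine, and only exclusion 21 is tied to the time of preparation. This weakens the comparison. A subject who knows of a new medicine may still not know that it matters, or may not be asked in time.

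**Other controls exist.** The investigator may withdraw a subject if an exclusion appears (10.15, item 5). MB-MMX is used per its label (10.3). Subjects can contact the investigator about a change in condition (10.12). Section 11.2 promises careful assessment before the procedure. None of these schedules a step that would detect a new medicine before intake. Subjects are asked about changes at visits, but no visit falls between V1 and V2. The subject instructions form and the consent form were not available. Either may already tell subjects to report new medicines, which would lower the risk without being a scheduled check.

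**The fix is selective.** Constipation medication (exclusion 12) and regular opioid use (exclusion 19) can also change. That is true, but it does not make a check of 15 and 17 unsound.

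**Dosing may be over.** SAP 7.1.3 describes both preparation regimens in the past tense, and protocol version 4.0 extended the study to allow procedures to be completed. This suggests, without proving, that few or no subjects remain to be dosed.

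**Conclusion.** The concern holds. The documents settle that no medication or eligibility check is scheduled in the 2 to 29 days before MB-MMX intake, and that the next review follows the full course. How often a barred medicine would be started, and how serious the result would be, cannot be determined from them; the percentages above depend on the assumed start and volunteering rates. The sample size and the planned analyses are not affected. The change should be made because it is cheap and enforces exclusions the protocol already contains. Confidence is medium, because the unseen subject forms may already reduce the risk.

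**What to change.** Add a concomitant-medication mark to the Preparation column of Table 1, with a footnote requiring a documented phone contact on day -1, before bowel preparation starts at 18:00. The call re-confirms exclusions 15 and 17 and is combined with the day -1 pregnancy test where that applies. If either exclusion is met (17 by label and investigator judgment), withhold MB-MMX and either withdraw the subject under 10.15 item 5 or postpone. Before a new date, re-confirm eligibility and repeat the day -1 call. Repeat screening if the new date is more than 30 days after V1. Tell subjects to call the site before starting any new medicine, if the forms do not already say so. Keep the day 0 entry.

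The cost is at most 15 short calls by existing staff, one mark and footnote, and one eCRF line. If only the 5 split-dose subjects in SAP 7.1.3 have been treated, at most 15 - 5 = 10 calls remain. It is a protocol amendment, so ethics committee approval, and regulatory approval where applicable, must come first (15.6). Changed subject-facing forms also need approval (14.1). A late cancellation could lose a subject who is not replaced (10.16), but the exclusions already bar that subject, and Appendix B already accepts cancelling or postponing for a preparation error. If dosing is complete, carry the check into the larger study mentioned in 6.2.

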## MDT20062 SPICE Clinical Investigation Plan Version 4.0 Version Date: 16Jun2022 Page 28 of 75 Medtronic

#### 10.2. Subject Screening (visit 1)

All subjects that are considered for the study should be included on the study screening log. The reason for non-eligibility, as determined by the Investigator, should be recorded on the study screening log. The screening log serves as a method for the Sponsor to assess selection bias in the trial.

During the screening visit, the investigator will obtain patient's written informed consent, after the subject had an ample time and opportunity to read and understand the ICF, verify that the subject does not have any contraindications for the PillCam™ Capsule Endoscopy procedure, and assess each subject for eligibility based on the inclusion/exclusion criteria.

To determine subject eligibility, baseline information will be collected as outlined in Table 1- Schedule of events and data collection:. Informed consent, vital signs, medical history, concomitant medications, urine pregnancy test (performed in women with childbearing potential) and demographic information will be collected during the visit. Study medications required for the preingestion procedure will be provided to eligible subjects during this visit.

Data of screen failure subjects will not be captured within the Electronic Case Report Form (eCRF). Their signed ICF and Inclusion-Exclusion criteria evaluation will be kept on site.

#### 10.3. PillCam™ Capsule pre-ingestion preparation procedure

The pre-ingestion preparation procedure is similar to colonoscopy or capsule endoscopy standard preparation and is performed in accordance to the labeling of the agents which are being used. In this study MB-MMX tablets will be also administrated to evaluate colonic polyps staining during the CCE procedure. Use of MB-MMX will be according to the product's label.

The preparation procedure will begin with a low fiber diet at days (-3)- (-2) before the CCE, followed by a clear liquid diet, starting from the day before capsule ingestion. At day (-1) prior to the CCE, a urine pregnancy test will be performed (as applicable and prior to prep/MB-MMX administration) and bowel preparation agent will be administrated (single dose) as well as administration of MB-MMX tablets (in accordance to the product's IFU). At the day of CCE procedure, 1 tablet of prucalopride (i.e. Resolor) 1mg will be administrated Prior to the CCE procedure. The subject will be required to consume additional bowel preparation & prokinetic agents during the CCE procedure.

Prior to the CCE procedure, the subjects will be given detailed instructions regarding the preparation regimen, as specified in the subject instructions form that will be provided to the subject during the screening visit.

